5.8 Survival Follow-Up

For all subjects, after disease progression, survival status, other malignancies, and subsequent anticancer therapy will be collected approximately every 12 weeks after the 30-day safety follow-up or the last visit when 30-day safety follow-up is not implemented until death by clinic visit or telephone call, withdrawal by the subjects, lost to follow-up, study discontinuation, or study termination by the Sponsor, whichever comes first.

5.9 Study Drug

Study drugs refer to drugs that are used (or can be used) in this study to assess the safety and the efficacy of the Investigational Product. Investigators will assess the relationship of adverse events to the use of study drugs (refer to Operations Manual Section 5.2, Table 2) for the list of study drugs.

Venetoclax tablets (10 mg, 50 mg, and 100 mg) and ibrutinib capsules (140 mg) will be provided by the Sponsor for oral administration once daily beginning on Day 1 and should be taken at approximately the same time each day with water within 30 minutes after the completion of a meal, preferably breakfast. Venetoclax tablets and ibrutinib capsules should be swallowed whole and not chewed, crushed, or broken prior to swallowing. If subjects should forget to take their venetoclax and/or ibrutinib dose at their regularly scheduled dosing time, they should take the forgotten dose as soon as they remember within 8 hours with a return to the normal schedule the following day. In cases of vomiting after taking study drug, no additional dose (tablets) should be taken that day.

Subject dosing will be recorded on a subject dosing diary. The subject will be instructed to return all drug containers (even if empty) to the study site personnel at each study visit. The study site personnel will document compliance.

Venetoclax and ibrutinib will be packaged in bottles with quantities sufficient to accommodate study design. Each kit will be labeled per local requirements and this label must remain affixed to the kit. Upon receipt, study drug should be stored as specified on the label and kept in a secure location. Each kit will contain a unique kit number. This kit number is assigned to a subject via interactive response technology (IRT) and encodes the appropriate study drug to be dispensed at the subject's corresponding study visit. Site staff will complete all blank spaces on the label before dispensing to subjects. Study drug will only be used for the conduct of this study.

Further information on study drug, packaging, labeling, etc. is provided in the Operation Manual, Section 6. Protocol instructions and information related to COVID-19, including direct-to-patient study drug shipment, are discussed in [Appendix I](#).

5.10 Drug Assignment

All subjects will be assigned a unique identification number by IRT at the screening visit. For subjects who rescreen, the screening number assigned by the IRT at the initial screening visit should be used. Subjects who are enrolled will retain their subject number assigned by IRT at the screening visit throughout the study and receipt of study drug will be acknowledged in the IRT system.

5.11 Protocol Deviations

AbbVie does not allow intentional/prospective deviations from the protocol except when necessary to eliminate an immediate hazard to study subjects. The investigator is responsible for complying with all protocol requirements, written instructions, and applicable laws regarding protocol deviations. If a protocol deviation occurs (or is identified, including those that may be due to the COVID-19 pandemic), the investigator is responsible for notifying IEC/IRB, regulatory authorities (as applicable), and AbbVie.

5.12 Independent Safety Monitor

The ISM will be a Japan medical oncologist with experience in clinical studies and who is familiar with the safety assessment of antitumor agents. To avoid any conflict of interest, the ISM must not be associated with or be an employee of the participating study institutions. The Sponsor will recommend subject enrolment based on the safety review and only if agreed by the ISM. Depending on the results of the safety review by ISM, revising the protocol will be considered where necessary. The ISM must be available for the AbbVie Clinical Team to contact for urgent evaluation of any safety issues. Detailed procedures for safety assessments will be described in a separately prepared document for operational procedures.

6 SAFETY CONSIDERATIONS

6.1 Complaints and Adverse Events

Complaints

A complaint is any written, electronic, or oral communication that alleges deficiencies related to the physical characteristics, identity, quality, purity, potency, durability, reliability, safety, effectiveness, or performance of a product/device. Complaints associated with any component of this investigational product must be reported to AbbVie.

Product Complaint

A product complaint is any complaint related to the biologic or drug component of the product or to the medical device component(s).

For a product this may include, but is not limited to, damaged/broken product or packaging, product appearance whose color/markings do not match the labeling, labeling discrepancies/inadequacies in the

labeling/instructions (e.g., printing illegible), missing components/product, device damage or not working properly, or packaging issues.

Product complaints concerning the investigational product and/or device must be reported to AbbVie within 24 hours of the study site's knowledge of the event.

Reporting will be done via electronic data capture (EDC). The date the product complaint details are entered into EDC and the form is saved represents the date reported to AbbVie. A back-up paper form will be provided for reporting complaints related to unassigned product or in the event of an EDC system issue. If a back-up paper form is used, the date the form is emailed to [contact] represents the date reported to AbbVie.

All follow-up information is to be reported to the Sponsor (or an authorized representative) and documented in source as required by the Sponsor. Product complaints associated with AEs will be reported in the study summary. All other complaints will be monitored on an ongoing basis. Product complaints occurring during the study will be followed up to a satisfactory conclusion.

Medical Complaints/Adverse Events and Serious Adverse Events

An AE is defined as any untoward medical occurrence in a subject or clinical investigation subject administered a pharmaceutical product and which does not necessarily have a causal relationship with this treatment. An AE can therefore be any unfavorable and unintended sign (including an abnormal laboratory finding), symptom, or disease temporally associated with the use of a medicinal (investigational) product, whether or not the event is considered causally related to the use of the product.

Such an event can result from use of the drug as stipulated in the protocol or labeling, as well as from "special situations" such as accidental or intentional overdose, medication error, occupational or accidental exposure, off-label use, drug abuse, drug misuse, or drug withdrawal, all which must be reported whether associated with an AE or not. Any worsening of a pre-existing condition or illness is considered an AE. Worsening in severity of a reported AE should be reported as a new AE. Laboratory abnormalities and changes in vital signs are considered to be AEs only if they result in discontinuation from the study, necessitate therapeutic medical intervention, meet protocol-specific criteria (see Section 6.2 regarding toxicity management), and/or if the investigator considers them to be AEs.

The investigators will monitor each subject for clinical and laboratory evidence of AEs on a routine basis throughout the study. All AEs will be followed to a satisfactory conclusion.

An elective surgery/procedure scheduled to occur during a study will not be considered an AE if the surgery/procedure is being performed for a pre-existing condition and/or the surgery/procedure has been pre-planned prior to study entry. However, if the pre-existing condition deteriorates unexpectedly during the study (e.g., surgery performed earlier than planned), then the deterioration of the condition for which the elective surgery/procedure is being done will be considered an AE.

If any TLS AEs are reported, the TLS supplemental report (electronic case report form [eCRF]) must be completed.

If an AE, whether associated with study drug or not, meets any of the following criteria, it is to be reported to AbbVie clinical pharmacovigilance as a serious adverse event (SAE) within 24 hours of the

site being made aware of the SAE (refer to Section 4.2 of the Operations Manual for reporting details and contact information):

Death of Subject	An event that results in the death of a subject.
Life-Threatening	An event that, in the opinion of the investigator, would have resulted in immediate fatality if medical intervention had not been taken. This does not include an event that would have been fatal if it had occurred in a more severe form.
Hospitalization or Prolongation of Hospitalization	An event that results in an admission to the hospital for any length of time or prolongs the subject's hospital stay. This does not include an emergency room visit or admission to an outpatient facility.
Congenital Anomaly	An anomaly detected at or after birth, or any anomaly that results in fetal loss.
Persistent or Significant Disability/Incapacity	An event that results in a condition that substantially interferes with the activities of daily living of a study subject. Disability is not intended to include experiences of relatively minor medical significance such as headache, nausea, vomiting, diarrhea, influenza, and accidental trauma (e.g., sprained ankle).
Important Medical Event Requiring Medical or Surgical Intervention to Prevent Serious Outcome	An important medical event that may not be immediately life-threatening or result in death or hospitalization, but based on medical judgment may jeopardize the subject and may require medical or surgical intervention to prevent any of the outcomes listed above (i.e., death of subject, life-threatening, hospitalization, prolongation of hospitalization, congenital anomaly, or persistent or significant disability/incapacity). Additionally, any elective or spontaneous abortion or stillbirth is considered an important medical event. Examples of such events include allergic bronchospasm requiring intensive treatment in an emergency room or at home, blood dyscrasias or convulsions that do not result in inpatient hospitalization, or the development of drug dependency or drug abuse.

All AEs reported from the time of study drug administration until 30 days after discontinuation of study drug administration will be collected, whether solicited or spontaneously reported by the subject. After 30 days following the last dose of study drug or completion of study treatment only spontaneously reported SAEs will be collected (nonserious AEs will not be collected). In addition, study procedure-related serious and nonserious AEs will be collected from the time the subject signs the study-specific informed consent.

Adverse Events of Special Interest

The following AEs of special interest will be monitored during the study:

- Tumor lysis syndrome
- Major hemorrhage

Tumor lysis syndrome events are defined as:

- Clinical TLS: any event that meets Howard criteria ([Appendix G](#)) with the following exceptions:
 - For the purpose of TLS assessment during the DLT evaluation period, only those increases in serum creatinine > 1.0 mg/dL from pre-treatment baseline will be considered clinical TLS.
 - In subjects with renal dysfunction at baseline (CrCl < 60 mL/min), clinical TLS is defined as the presence of laboratory TLS plus either seizures, cardiac dysrhythmia, or death.
- Laboratory TLS: any event that meets Howard criteria ([Appendix G](#)) for laboratory TLS, that does not resolve within 72 hours despite protocol required management.

Major hemorrhage events are defined as:

- Any treatment-emergent Grade \geq 3 hemorrhage AEs (all hemorrhagic events requiring transfusion of red blood cells should be reported as Grade 3 or higher AE per National Cancer Institute (NCI) CTCAE v5.0).
- Any treatment-emergent SAEs of bleeding of any grade
- Any treatment-emergent CNS hemorrhage/hematoma of any grade.

Adverse Event Severity and Relationship to Study Drug

The investigator will rate the severity of each AE according to the NCI CTCAE Version 5.0. If a reported AE increases in severity, the initial event should be given an outcome date and a new AE must be reported to reflect the change in severity. For all reported SAEs that increase in severity, the supplemental eCRFs also need to be updated to reflect any changes due to the increase in severity.

For AEs not captured by the NCI CTCAE, the following criteria should be used:

Grade 1	Mild; asymptomatic or mild symptoms; clinical diagnostic observations only; intervention not indicated.
Grade 2	Moderate; minimal, local or noninvasive intervention indicated; limiting age-appropriate instrumental activities of daily living.
Grade 3	Severe or medically significant but not immediately life-threatening; hospitalization or prolongation of hospitalization indicated; disabling; limiting self-care activities of daily living.
Grade 4	Life-threatening consequences; urgent intervention indicated.
Grade 5	Death related to adverse event.

The investigator will use the following definitions to assess the relationship of the AE to the use of study drug (venetoclax and ibrutinib):

Reasonable Possibility	After consideration of factors including timing of the event, biologic plausibility, clinical judgment, and potential alternative causes, there is sufficient evidence (information) to suggest a causal relationship.
No Reasonable Possibility	After consideration of factors including timing of the event, biologic plausibility, clinical judgment, and potential alternative causes, there is insufficient evidence (information) to suggest a causal relationship.

Pregnancy

While not an AE, pregnancy in a study subject must be reported to AbbVie within 24 hours after the site becomes aware of the pregnancy. Subjects who become pregnant during the study must be discontinued (Section 5.6). If a pregnancy occurs in a study subject or in the partner of a study subject, information regarding the pregnancy and the outcome will be collected.

In the event of pregnancy occurring in a subject's partner during the study, written informed consent from the partner must be obtained prior to collection of any such information. AbbVie will provide a separate consent form for this purpose. Pregnancy in a subject's partners will be collected from the date of the first dose through 90 days following the last dose of study drug.

The pregnancy outcome of an elective or spontaneous abortion, stillbirth or congenital anomaly is considered a SAE and must be reported to AbbVie within 24 hours after the site becomes aware of the event.

6.2 Toxicity Management

Venetoclax

Dose Modification for Adverse Reactions

Venetoclax dosing interruption and/or dose reduction may be required. See [Table 2](#) for dose modifications for hematologic and other toxicities related to venetoclax. For subjects who have had a dosing interruption greater than 1 week during the ramp-up period or greater than 2 weeks when at target dose, reassess for risk of TLS to determine if re-initiation with a reduced dose is necessary. Venetoclax dose reduction is not allowed during the DLT assessment period.

Table 2. Recommended Dose Modifications for Venetoclax-Related Toxicities

Event	Occurrence	Action
Tumor Lysis Syndrome Blood chemistry changes or symptoms suggestive of TLS	Any	Withhold the next day's dose. If resolved within 24 to 48 hours of last dose, once the toxicity has resolved to Grade 1 or baseline level, resume at the same dose.
		For any blood chemistry changes requiring more than 48 hours to resolve, once the toxicity has resolved to Grade 1 or baseline level, resume at a reduced dose ^a (see Table 3)
		For any events of clinical TLS, once the toxicity has resolved to Grade 1 or baseline level, resume at a reduced dose following resolution (see Table 3)
Non-Hematologic Toxicities Grade 3 or 4 non-hematologic toxicities	First	Interrupt venetoclax Once the toxicity has resolved to Grade 1 or baseline level, venetoclax therapy may be resumed at the same dose. No dose modification is required.
	Second and subsequent	Interrupt venetoclax Once the toxicity has resolved to Grade 1 or baseline level, resume at a reduced dose following resolution (see Table 3). A larger dose reduction may occur at the discretion of the investigator.
Hematologic Toxicities Grade 3 or 4 neutropenia with infection or fever; or Grade 4 hematologic toxicities (except lymphopenia)	First	Interrupt venetoclax. To reduce the infection risks associated with neutropenia, G-CSF may be administered with venetoclax if clinically indicated. Once the toxicity has resolved to Grade 1 or baseline level, venetoclax may be resumed at the same dose. ^a
	Second and subsequent occurrence	Interrupt venetoclax. Consider using G-CSF as clinically indicated. Once the toxicity has resolved to Grade 1 or baseline level, resume at a reduced dose following resolution ^a (see Table 3). A larger dose reduction may occur at the discretion of the investigator.

DLT = dose limiting toxicity; G-CSF = granulocyte-colony stimulating factor; TLS = tumor lysis syndrome

a. Venetoclax dose reduction is not allowed during the DLT assessment period.

Consider discontinuing venetoclax for subjects who require dose reductions to less than 100 mg for more than 2 weeks.

If the dose of venetoclax is reduced, at the investigator's discretion, the dose of venetoclax may be re-escalated after 2 months of a dose reduction in the absence of a recurrence of the toxicity that led to the reduction. Subsequent dose re-escalations should be discussed with the AbbVie TA MD.

Table 3. Dose Modification for Toxicity During Venetoclax Treatment

Dose at Interruption	Restart Dose ^a
400 mg	300 mg
300 mg	200 mg
200 mg	100 mg

a. Continue the reduced dose for at least 1 week before increasing the dose.

Prophylaxis and Management of Tumor Lysis Syndrome

Venetoclax can cause rapid reduction in tumor and thus poses a risk for TLS in the ramp-up period. Changes in electrolytes consistent with TLS that require prompt management can occur as early as 6 to 8 hours following the first dose of venetoclax and at each dose increase. The risk of TLS is a continuum based on multiple factors, including comorbidities. Subjects with high tumor burden are at greater risk of TLS when initiating venetoclax. Reduced renal function further increases the risk. The risk may decrease as tumor burden decreases with continued venetoclax treatment.

Tumor burden assessments, including radiographic evaluation (e.g., CT scan) should be performed at Screening as well as blood chemistry assessments (potassium, phosphorus, calcium, uric acid, creatinine, lactate dehydrogenase, and, if available, albumin, corrected calcium, and ionized calcium) in all subjects. Pre-existing abnormalities should be corrected prior to initiation of treatment with venetoclax.

- High risk for TLS: Subjects with high tumor burden (at least one lesion > 10 cm; or at least one lesion > 5 cm **and** circulating lymphocytes > 25,000 cells/mm³) and/or with baseline CrCl < 60 mL/min.
- Low risk for TLS: Subjects not meeting the criteria described above.

The prophylaxis measures listed below should be followed and more intensive measures (including hospitalization) should be employed for subjects at high-risk for TLS based on local guidelines or institutional standards:

- Hydration: Ensure adequate hydration (1.5 L to 2 L) 48 hours prior to initiating therapy with venetoclax and throughout the ramp-up period, especially on the first day of each ramp-up dose. Administer IV fluids as indicated based on the overall risk of TLS or for those who cannot maintain adequate oral hydration.
- Anti-hyperuricemic agents: Administer anti-hyperuricemic agents (e.g., allopurinol) within 72 hours prior to initiation of venetoclax; consider continuing through the ramp-up period. Rasburicase is recommended for subjects at high-risk, especially those with high tumor burden.
- Laboratory Assessments:
 - Pre-dose: Assess blood chemistries prior to initiating venetoclax to evaluate kidney function and correct pre-existing abnormalities. Reassess blood chemistries before starting each subsequent ramp-up dose of venetoclax.

- Post-dose: **For hospitalized subjects**, monitor blood chemistries 4 hours, 8 hours, 12 hours, 24 hours and, as needed, 48 hours after the venetoclax dose. **For outpatient subjects**, monitor blood chemistries at 6 to 8 hours and at 24 hours after the venetoclax dose. Electrolyte abnormalities should be corrected promptly (see [Appendix G](#)). **The next dose of venetoclax should not be administered until the 24 hour blood chemistry results have been evaluated.** The monitoring schedule should be followed in the Operations Manual ([Appendix K](#)) when starting each subsequent ramp-up dose. Refer to [Appendix G](#) for definitions of laboratory and clinical TLS.
- Subjects at low risk of TLS may have laboratory assessments conducted on an outpatient basis. If low risk subjects are hospitalized for logistical reasons, laboratory assessments will be conducted per the outpatient schedule.
- Hospitalization: Based on investigator assessment, subjects with a high-risk of TLS require hospitalization at the 20 mg and the 50 mg ramp-up doses of venetoclax for more intensive prophylaxis and monitoring. The timing of discharge from hospital will be decided based on investigator assessment of available data at that time. Consider hospitalization for subsequent ramp-up doses based on the reassessment of risk. Subjects at low risk of TLS may also be hospitalized, at the investigator's discretion. During the course of the study, the investigators and Sponsor will review TLS data to determine whether continued hospitalization of these subjects is warranted.

Ibrutinib

Dose Modification for Adverse Reactions

Ibrutinib interruption and/or dose reduction may be required for toxicities related to ibrutinib. The dose of study drug must be modified according to the dose modification guidance in [Table 4](#) and [Table 5](#) if any of the following ibrutinib related toxicities occur:

- Grade 3 or greater neutropenia with infection or fever
- Grade 4 neutropenia (ANC < 500/ μ L) for more than 7 days
- Grade 3 thrombocytopenia (platelets < 50,000/ μ L) in the presence of Grade \geq 2 bleeding
- Grade 4 thrombocytopenia (platelets < 25,000/ μ L)
- Grade 3 or greater non-hematological toxicity (Note: [Table 5](#) recommendations for Grade 3 or greater cardiac failure and cardiac arrhythmias)
- Grade 2 cardiac failure ([Table 5](#))
- Any other Grade 4 or unmanageable Grade 3 toxicity.

If clinically indicated, the use of anticoagulants or antiplatelet agents should be considered for the thromboprophylaxis of atrial fibrillation.

Dose changes must be recorded in the Dose Administration eCRF. Ibrutinib dose reduction is not allowed during the DLT assessment period.

Table 4. Ibrutinib Dose Modifications for Toxicities

Event	Occurrence	Action
Hematologic Toxicities (neutrophil decrease and platelet decrease)	First	Withhold ibrutinib until recovery to an ANC \geq 750/ μ L or platelets $>$ 25,000/ μ L with no evidence of Grade \geq 2 bleeding; may restart at the same dose level.
	Subsequent	Withhold ibrutinib until recovery to an ANC \geq 750/ μ L or platelets $>$ 25,000/ μ L with no evidence of Grade \geq 2 bleeding; may restart at 1 dose level lower (refer to Table 6).
Other Hematologic and Non-Hematological Toxicities (for events not specified in Table 5)	First	Withhold ibrutinib until recovery to Grade \leq 1 or baseline; may restart at the same dose level. ^a
	Second	Withhold ibrutinib until recovery to Grade \leq 1 or baseline; restart at 1 dose level lower (i.e., 420 mg daily) (refer to Table 6).
	Third	Withhold ibrutinib until recovery to Grade \leq 1 or baseline; restart at 1 dose level lower (i.e., 280 mg daily) (refer to Table 6).
	Fourth	Discontinue ibrutinib

ANC = absolute neutrophil count; DLT = dose limiting toxicity

a. When resuming treatment, restart at the same or lower dose based on benefit-risk evaluation. If the toxicity reoccurs, reduce daily dose by 140 mg.

Notes:

- Ibrutinib dose reduction is not allowed during the DLT assessment period.
- Do not dose below 280 mg daily except in case of required concomitant administration of strong or moderate CYP3A inhibitors or moderate hepatic impairment.
- Refer to [Table 5](#) for Ibrutinib Dose Modifications for Cardiac Failure or Cardiac Arrhythmias.

Table 5. Ibrutinib Dose Modifications for Cardiac Failure or Cardiac Arrhythmias

Event	Occurrence	Action
Grade 2 cardiac failure	First	Hold ibrutinib until recovery to Grade ≤ 1 or baseline; restart at 1 dose level lower (i.e., 420 mg daily)
	Second	Hold ibrutinib until recovery to Grade ≤ 1 or baseline; restart at 1 dose level lower (i.e., 280 mg daily)
	Third	Discontinue ibrutinib
Grade 3 cardiac arrhythmias	First	Hold ibrutinib until recovery to Grade ≤ 1 or baseline; restart at 1 dose level lower (i.e., 420 mg daily) ^a
	Second	Discontinue ibrutinib
Grade 3 or 4 cardiac failure; Grade 4 cardiac arrhythmias	First	Discontinue ibrutinib

a. Evaluate the benefit-risk before resuming treatment.

Notes:

- Ibrutinib dose reduction is not allowed during the DLT assessment period.
- Refer to [Table 4](#) for additional ibrutinib dose modifications.

Table 6. Ibrutinib Dose Reduction Levels

Starting Dose Level	560 mg
Dose Reduction Level 1	420 mg
Dose Reduction Level 2	280 mg
Dose Reduction Level 3	140 mg
Dose Reduction Level 4	Discontinue

Leukocytosis/Leukostasis

A high number of circulating white blood cells (> 400,000/µL) may confer increased risk of leukostasis; these subjects should be closely monitored. Administer supportive care such as hydration and/or leukapheresis as indicated. Ibrutinib may be temporarily held.

Dose Modification for Hepatic Impaired Subjects

Ibrutinib is metabolized in the liver, and therefore subjects with clinically significant chronic hepatic impairment at Screening (Child-Pugh class B or C) are excluded from study participation.

- For subjects with existing chronic mild hepatic impairment (Child-Pugh class A) at enrollment, the starting dose will be adjusted to a level of 280 mg daily (two capsules).
- For subjects who develop mild hepatic liver impairment while on study (Child-Pugh class A), the recommended dose reduction for ibrutinib is to a level of 280 mg daily (two capsules) unless lower doses had already been implemented.

- Subjects who develop moderate or severe hepatic impairment while on study (Child-Pugh class B or C) must hold study drug(s) until resolved to mild impairment (Child-Pugh class A) or better.
- Subjects who develop acute hepatic toxicity with liver enzymes Grade 3 or higher while on study should be managed per standard dose modification guidelines.

Table 7. Child-Pugh Score for Subjects with Liver Impairment^{33,34}

Measure	1 point	2 points	3 points
Total bilirubin, μ mol/L (mg/dL)	< 34 (< 2)	34 to 50 (2 to 3)	> 50 (> 3)
Serum albumin, g/L (g/dL)	> 35 (> 3.5)	28 to 35 (2.8 to 3.5)	< 28 (< 2.8)
PT/INR	< 1.7	1.71 to 2.30	> 2.30
Ascites	None	Mild	Moderate to Severe
Hepatic encephalopathy	None	Grade I to II (or suppressed with medication)	Grade III to IV (or refractory)
Points	Class		
5 to 6	A		
7 to 9	B		
10 to 15	C		

INR = international normalized ratio; PT = prothrombin time

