If one or more electrolyte changes suggestive of TLS occur within 24 hours of the 20 mg dose, no additional venetoclax doses will be administered until resolution. If correction of electrolytes abnormalities is performed, the subsequent dose of venetoclax can only be given when electrolytes have been stable without any more treatment for at least 24 hours. Refer to [Table 2](#), Recommended Dose Modifications for Venetoclax-Related Toxicities, for additional TLS management guidelines. Upon resolution of laboratory abnormalities, the subject will resume at the ramp-up dose. When venetoclax dose interruptions are required during the ramp-up period, the next highest dose level may be initiated 7 days from the start of the current dose level, once the toxicity has resolved to Grade 1 or baseline level and at the investigator's discretion. At the investigator's discretion, the duration of a single dose level during the ramp-up period may be longer than 7 days before increasing to the next highest dose level.

For all ramp-up doses, laboratory values for subject management must be reviewed in real time by the investigator or designee, and prior to the subject's next dose, to ensure appropriate subject management. Based on the laboratory values, the subject may continue dosing, may need to hold dose until resolution, may require hospitalization for further monitoring, or may need additional post-dose laboratory checks.

Initially, subjects at high-risk for TLS will be hospitalized at the start of the venetoclax 20 mg ramp-up dose and again at the start of the 50 mg ramp-up dose for monitoring and prophylaxis of TLS. Subjects will be considered as high-risk for TLS if they have a high tumor burden (at least one lesion > 10 cm; or at least one lesion > 5 cm and circulating lymphocytes > 25,000 cells/mm³) and/or with baseline creatinine clearance (CrCl) < 60 mL/min. Subjects not meeting the high-risk criteria will be considered low risk for TLS. Subjects will be discharged from hospital if there is no evidence of TLS. AbbVie will review the safety data during the course of the study to determine whether continued hospitalization of subjects at high-risk for TLS during ramp-up remains warranted.

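### Venetoclax restart instructions after TLS conflict in two situations: clinical TLS in the DLT period, and slow or clinical TLS after the 20 mg dose

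*Protocol*

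**What the plan says.** Three sets of instructions in the current protocol bear on the dose at which venetoclax restarts after TLS.

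- **Section 4.1.** The trigger is "If one or more electrolyte changes suggestive of TLS occur within 24 hours of the 20 mg dose". Dosing is held, and then "Upon resolution of laboratory abnormalities, the subject will resume at the ramp-up dose". No limit on the time to resolution is attached. The reader is also sent to Table 2, described as "Recommended Dose Modifications for Venetoclax-Related Toxicities, for additional TLS management guidelines". Neither place says which governs if they differ.
- **Section 6.2, Table 2, TLS rows.** There are three cases. "If resolved within 24 to 48 hours of last dose" leads to the same dose. "For any blood chemistry changes requiring more than 48 hours to resolve" leads to a reduced dose and carries footnote a. Clinical TLS reads "For any events of clinical TLS, once the toxicity has resolved to Grade 1 or baseline level, resume at a reduced dose following resolution" and carries no footnote. Both reduced-dose rows refer to Table 3, "Dose Modification for Toxicity During Venetoclax Treatment", whose rows cover interruption at 400, 300 and 200 mg.
- **Section 6.2, text above Table 2, repeated as footnote a.** "Venetoclax dose reduction is not allowed during the DLT assessment period". No exception is made for TLS.

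Section 6.3 has DLTs assessed in the first 6 subjects through the ramp-up, for at least 5 weeks and including at least 1 week at 400 mg. Section 6.1 gives a special creatinine threshold for calling clinical TLS within that period, so the protocol foresaw the event there.

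**The concern.** TLS is the acute risk that the ramp-up is designed to control, and Section 6.2 itself places the risk in the ramp-up. For some events a site would find one instruction to reduce the dose and another that forbids a reduction or returns the subject to the same level. Two sites could then handle the same event differently and both claim to have followed the protocol. In the first 6 subjects that would also blur what the tolerability assessment describes, because the dosing behind it would depend on which instruction the site read. No power, alpha or response-rate calculation depends on this point; it is an internal inconsistency in safety instructions.

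**Working it through.** No planned statistical figure rests on these instructions, so the check is a side-by-side reading of the rules.

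**Does ramp-up TLS fall inside the DLT period?** Section 4.1 gives five levels (20, 50, 100, 200, 400 mg) at 7 days each: 5 × 7 = 35 days = 5 weeks, equal to the stated minimum. If the ramp-up runs longer, the period extends with it, because a week at 400 mg is required. So for the first 6 subjects every ramp-up TLS event falls inside the period.

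**Which rules apply to which event?** I take resuming at the ramp-up dose in Section 4.1 to mean the current level, 20 mg. Outside the DLT period means subjects after the first 6.

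| Event | 20 mg, DLT period | 20 mg, outside | 50 to 400 mg, DLT period | 50 to 400 mg, outside |
|---|---|---|---|---|
| Resolved within 24 to 48 h | agree | agree | agree | Table 2 only |
| More than 48 h | Table 2 row differs from 4.1; footnote a removes the reduction | Table 2 against 4.1 | settled by footnote a | Table 2 only |
| Clinical TLS | Table 2 against 4.1 and against the bar | Table 2 against 4.1 | Table 2 against the bar | Table 2 only |

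The grid has 5 levels × 3 event types × 2 periods = 30 combinations.

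- Clinical TLS in the DLT period: 5 conflicts, one per level.
- 20 mg outside the DLT period: 2 conflicts (more than 48 hours, and clinical).
- Total: 5 + 2 = 7. It becomes 8 if the more-than-48-hour row at 20 mg in the DLT period is read without its footnote.

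These are counts of rule combinations, not of expected events. The clinical TLS entries at 20 mg assume that the electrolyte changes arise within 24 hours. Appendix G makes laboratory TLS a component of clinical TLS, so such a subject can meet the Section 4.1 trigger.

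**Can a reduced dose be looked up?** Ramp-up levels {20, 50, 100, 200, 400} minus Table 3 rows {400, 300, 200} leaves {20, 50, 100}: 3 of 5 levels have no restart entry. Section 6.2 also speaks of reductions below 100 mg, although the lowest restart dose shown in Table 3 is 100 mg.

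**How often might this arise?** From Protocol Sections 2.1 and 4.2:

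- AIM, 50 mg start: 2 of 16 = 12.5%, which matches the 13% in Section 4.2.
- AIM, revised 20 mg start: 0 of 8.
- SYMPATICO run-in, whose regimen this study adopts: 1 laboratory event in 21 (1/21 = 4.8%) and no clinical event. For 0 of 21 the upper limit of the exact two-sided 95% interval is 1 − 0.025^(1/21) = 0.161, so these data do not exclude a clinical TLS rate of up to about 16%.

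**The case against.** The best defence is that the bar is a general prohibition, stated without exception directly above a table whose title calls its contents recommended. It need not be repeated in every row. Footnote placement is weak evidence of intent, since the mark is irregular elsewhere: it sits on the first-occurrence hematologic row, which keeps the same dose, and is absent from the later-occurrence non-hematologic row, which reduces it. Section 4.1 does send the reader to Table 2. Section 6.2 also asks for TLS risk to be reassessed after a ramp-up interruption longer than 1 week, to see whether a reduced restart is needed.

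Most of this stands as a possible reading, but it does not remove the conflict. One TLS row is marked and the adjacent one is not, so a site cannot tell an exemption from an omission. No section states precedence. One might argue that a TLS event counted as a DLT ends that subject's assessment period and so lifts the bar. Section 6.3 hints at this by treating non-completion because of a DLT separately, but no section says it.

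Three stronger inferences are tempting and are not supported:

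- **Every TLS event in the first 6 subjects meets three clashing rules.** Section 4.1 covers only electrolyte changes soon after the 20 mg dose. The 24-to-48-hour row agrees with the other rules, and footnote a settles the more-than-48-hour row in the DLT period. Section 4.1 and the bar agree with each other; it is Table 2 that differs from each.
- **The conflict puts DLT evaluability at risk.** Section 6.3 makes a subject non-evaluable for not completing the period for reasons other than a DLT. A TLS event that qualifies as a DLT therefore does not cost evaluability by preventing the week at 400 mg.
- **The AIM figure of 2 in 16 shows the risk here.** It comes from a starting dose since abandoned. The 0 of 8 and the SYMPATICO results are closer to this regimen.

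**Conclusion.** The inconsistency is real and confined to two situations. First, for clinical TLS in the DLT period, Table 2 and the bar on reduction cannot both be followed at any of the 5 ramp-up levels. Second, after the 20 mg dose, Section 4.1 and Table 2 disagree when resolution takes more than 48 hours or TLS is clinical. In the DLT period, footnote a removes the disagreement for the more-than-48-hour case if it is read as leaving the dose unchanged.

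The gap in Table 3 adds to the difficulty but is conditional: it assumes that no row was lost when the public PDF was converted to text. The remark about the unmarked clinical TLS row likewise assumes that the superscripts survived conversion. The first conflict does not depend on either assumption, because the sentence above Table 2 states the bar by itself.

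The consequence today is limited. SAP Section 9.1 reports that the first 6 subjects were evaluated and full enrollment was recommended, and Protocol Appendix J states that the primary analysis is complete. What remains is contradictory safety text in a protocol still in force, and the need to be clear about how any TLS event in those subjects was handled. Which instruction is clinically right is not a matter for this review.

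**What to change.** Reconcile Section 4.1 with Section 6.2 (text, Table 2 and footnote a) so that each TLS event has one restart instruction. Specifically:

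- State whether the DLT-period bar covers TLS events.
- Make the footnote placement consistent across the TLS rows of Table 2.
- State which text governs where Section 4.1 and Table 2 both apply.
- Check that Table 3 covers every dose level to which Table 2 sends the reader.

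The clinical team decides the content of the rule.

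For the first 6 subjects, amended wording cannot change what was done. The study report should record whether any TLS event occurred in the DLT period and, if so, which instruction was applied.

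The cost is a wording and table amendment plus a short note in the report. No analysis, sample size or data collection changes.
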